9.17.2 Study Completed

At the completion of the 30-day follow-up visit, subjects will be exited from the study. The 30-day follow-up visit and exit visit should be combined, and both a 30-day Subject Visit CRF and a Study Exit eCRF need to be completed.

9.17.3 Lost to Follow-up

A subject is considered to be lost to follow-up if at least two attempts to contact the subject are unsuccessful. The method of attempt (e.g., one letter and one phone record, or two letters) must be documented in the subject's medical record. In addition, regulation set forth by the governing IRB/REB must be followed.

9.17.4 Subject Chooses to Exit (i.e. Revokes Consent)

A subject can withdraw from the study at any time. If the subject wishes to exit from the study (i.e. the subject revokes consent), the study site is required to document the reason for exit on the Study Exit CRF. In addition, study sites shall follow the regulations set forth by the governing IRB/RCB. If possible, the following data should be collected prior to subject withdrawal:

- Date of study exit
- Reason for exit

9.17.5 Investigator Withdraws Subject

No subjects should be withdrawn by investigators unless compelling medical justification is present. It is recommended investigators discuss any withdrawals with the study team prior to withdrawing subjects.

Medtronic Business Restricted

Early removal of Novapak (within the first 7 days of application) alone may not be a reason for subject withdrawal. If an Investigator Withdrawal is necessary, the following data should be collected prior to subject withdrawal if possible:

- Date of study exit
- Reason for subject withdrawal

10. Risks and Benefits

10.1 Potential Risks

Medtronic follows rigorous Quality Assurance and Control procedures throughout the life of a product, from the business analysis phase through development, market release, and post-market surveillance. The risk analysis process for the Novapak Study, is being performed in accordance with ISO 14971 and will ensure that the level of risk is acceptable prior to starting the study.

There are no incremental risks introduced to the subject as a result of participation in this study.

There are inherent risks for nasal sinus surgery as well as any surgery where removal, cutting and modification of tissues are required. These risks include:

- Mild Bleeding
- Adhesions, tissue synechia
- Fatigue
- Infection
- Moderate Pain
- Inflammation and swelling
- Nasal Congestion
- Mild to moderate headaches
- Facial pressure

Nasal sinus packing in general has tried to address these surgical complications but may result in risks that are specific to the use of packing, as follows:

- Bleeding – present if packing is inadequate or bleeding is excessive– may require post-operative controls (e.g., suturing, cautery, more packing)
- Adhesions – present if packing is inadequate to separate tissue compromised due to surgical trauma – requires post-operative debridement of tissues which may lead to bleeding.
- Scarring - This risk is where the tissue heals abnormally

- Infection – due to introduction of bacterial during the surgery and/or if sterility is breached - packing could encourage bacterial growth if design controls are not in place to control bacterial growth.
- Toxic Shock Syndrome –defined as “A severe illness caused by infection with staphylococcus aureus and characterized by high fever of sudden onset, vomiting, diarrhea, and myalgia, followed by hypotension and in severe cases, shock; a sunburn like rash with peeling of the skin, especially of the palms and soles, occurs during the acute phase.”
- Respiratory Obstruction – physical obstruction of the breathing pathway – This harm may occur from stent migration and cause difficulty breathing (i.e., hypoxia, dyspnea)
- Aspiration of the packing – causes respiratory obstruction with tachypnea can lead to aspiration pneumonia, urgent medical intervention may be necessary
- Pneumonia - If the stent were aspirated, pneumonia may occur. The patient may be treated with IV medication.
- Potential toxicity reactions – components of the packing could lead to a toxicity reaction due to a non-biocompatibility reaction occurring, but the reaction would not be expected to go beyond an inflammatory response. (i.e., redness, swelling, etc.)
- Potential allergic hypersensitivity reactions – components of the packing could lead to an allergic hypersensitivity reaction - A patient may experience edema and difficulty breathing with IV medications used as medical intervention.
- Foreign Body Reaction - Potential tissue interactions with packing components, fragments, or surface texture. In addition to an inflammatory response, it usually includes the formation of a foreign body granuloma, or encapsulation around a foreign object. Medical intervention may be taken to remove the product.
- Inflammation - This harm includes local irritation from the product. This risk may require Oral medication to reduce inflammatory response.
- Fever - A medium-low grade fever may develop. This risk may require Oral medication to reduce inflammatory response.
- Device Fragments in Patient – If a device fragments migration of pieces of the stent could result in possible medical intervention needed
- Pain – during post-operative removal of non-dissolving packing devices most patients have reported some mild temporary pain.
- Decreased Therapeutic Response – The packing may not perform as expected and not control the risks as intended. It would not result in surgical correction but may require a minor medical intervention.

The use of the Novapak Nasal Sinus Packing and Stent may involve the risks listed above for all packing type devices, with the exception of pain upon removal, since it dissolves away with irrigation. There may be other discomforts and risks related to the Novapak Nasal Sinus Packing and Stent device and/or this study that are not foreseen at this time.

Medtronic Business Restricted

These are the current risks of Novapak seen in the field based on reports to our complaint system: (number of reported events as of June 24, 2022)

- Irritation – potential shellfish hypersensitivity (1)
- Post-operative bleeding requiring secondary controls (3)
- Post-operative device migration to oral cavity (1)
- Post-operative edema and pain (2)

10.2 Risk Minimization

The potential risks associated with the Novapak device were identified and have been successfully mitigated. Any potential risks associated with this study are further minimized by selecting qualified investigators and training study personnel on the CIP.

In addition, investigators will be actively involved in the nasal sinus surgery and follow-up of the subjects using the Novapak device.

Risks will be minimized by careful assessment of each subject prior to, during and after surgery, and during and after application of the Novapak Nasal Sinus Packing and Stent device. Prior to surgery, each subject will be screened for shellfish allergy to mitigate the risk of a hypersensitivity reaction to the chitosan component of the device. It is recommended subjects undergo a complete physical evaluation.

Medtronic has further minimized the possibility of risks by: performing required laboratory and pre-clinical testing prior to the Novapak study, implementing quality control measures into production processes, providing guidelines for subject selection and evaluation, and providing adequate instructions and labeling.

After surgery, subjects in the Novapak Study will be followed at regular intervals to monitor the condition of the nasal sinus healing process. At each protocol required follow-up, the investigator must assess any adverse events.

Table 7: Potential risks and risk minimization

Potential risk	Risk Minimization
Hypersensitivity	Screening for shellfish allergy
Infection	Design controls – device component has an antimicrobial effect

10.3 Potential Benefits

The Novapak Device is used for nasal packing to prevent bleeding after sinus surgery and may offer no benefit. The potential benefits of having the Novapak Nasal Sinus Packing and Stent device include control of minimal bleeding, prevent post-surgical adhesions by acting as a space occupying stent which separates tissues compromised by surgical trauma, aid in the natural healing process, eliminate the need for packing removal by dissolving away with irrigation. These potential benefits aid the patient as well as the physician by providing a tool to manage common post-surgical effects (i.e. bleeding,

Medtronic Business Restricted

adhesions and removal of packing). Additionally, information collected from this study may assist in the design of new products/therapies and/or IFU.

10.4 Risk-Benefit Rationale

The use of the Novapak device does not appear to add unreasonable risks to the common technique of nasal packing post nasal sinus surgery. Benefits of nasal packing with the Novapak device (Section 10.3) when used by a trained physician greatly outweigh any risks associated with this therapy (Section 10.1).

10.5 Risk Determination

The Novapak device is commercially available in the US and Canada. The device was cleared for use under US FDA 510(k) number K202623 on December 08, 2020, and this study is therefore exempt per US FDA 21 CFR 812. The device is licensed for use in Canada under license number 103651 issued September 25, 2019.

11. Adverse Events and Device Deficiencies

This section describes how Adverse Events and Device Deficiencies will be handled in this study.

11.1 Adverse Events

AE definitions are provided in **Table 9**. All AE information will be collected throughout the study duration, starting during sinus surgical procedure and treatment with the Novapak device and concluding with the 30-day visit and/or study exit (whichever occurs first).

Reporting of these events to Medtronic will occur on an AE eCRF. Each event must be reported separately. Documented pre-existing conditions are not considered AEs unless the nature or severity of the condition has worsened.

In all geographies, UAEs occurring post-surgery need not be reported unless the adverse event worsens or is present outside the stated timeframe post-surgery.

Table 8: Post-Surgery Unavoidable Adverse Events

Event Description	Timeframe – days after surgical procedure
Sudden visual changes or ocular swelling	1
Fever higher than 101°F	1
Anesthesia related complications	2
Medication related complications	2
Mild bleeding (bloody discharge)	5
Constant clear watery discharge	7
Facial pressure	7
Fatigue	7
Inflammation and swelling	7

Medtronic Business Restricted

Mild to moderate headaches	7
Moderate pain	7
Numbness of the Teeth or Palate	7
Nasal congestion	10

For AEs that require immediate reporting (see **Table 11**), initial reporting may be done by email or phone, or on the eCRF completing as much information as possible. The completed AE eCRF must be submitted to Medtronic as soon as possible.

Any medication/treatment associated with the treatment of an AE must be reported.

Subject deaths are also required to be reported. Refer to Section 11.6 for Subject Death collection and reporting requirements.

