4.1.1.1.1 Primary Device Safety Endpoints

The primary safety endpoint is an assessment of all AEs that are directly attributable to the device and/or for which cause cannot be determined, and that meet the definition of designated primary safety endpoint AEs (see section 11.4) that will be used to determine the point estimate and its confidence interval. This endpoint will be analyzed by calculating the point estimate with a confidence interval of its rate. All AEs will be collected for each subject from time of treatment until their study completion.

Study completion for each subject is the time point at which the 30-day follow-up visit is completed, outstanding AE follow-up (if any) has been concluded, and a Study Exit CRF has been completed. For subjects who withdrew or were lost to follow-up, study completion will be the date of withdrawal or the date the subject meets the definition of lost to follow-up. Refer to **Section 13** for how missing data will be handled.

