11.4 Definitions/Classifications

Where the definition indicates “device”, it refers to only the device under investigation used in the study.

Table 9: Adverse Event and Device Deficiency Definitions

General	
Adverse Event	An untoward medical occurrence, unintended disease or injury, or untoward clinical signs in subjects, users or other

Medtronic Business Restricted

	
persons, whether or not related to the investigational medical device and whether anticipated or unanticipated.
 
NOTE: This definition includes events related to the investigational medical device.
 
NOTE: This definition includes events related to the procedures involved.
 
NOTE: for users or other persons, this definition is restricted to events related to the use of investigational medical devices.

Adverse Device Effect (ADE)	
Adverse event related to the use of an investigational medical device.
 
NOTE: This definition includes adverse events resulting from insufficient or inadequate instructions for use, deployment, implantation, installation, or operation or any malfunction of the investigational medical device.
 
NOTE: This definition includes any event resulting from use error or from intentional misuse of the investigational medical device.

Device Deficiency	
Inadequacy of a medical device with respect to its identity, quality, durability, reliability, usability, safety or performance.
 
NOTE: Device deficiencies include malfunctions, use errors, and inadequacy in the information supplied by the manufacturer including labeling.

Relatedness - Procedure	
An event that occurs as a result of the nasal sinus surgical procedure(s). This includes events involving devices used in the surgical procedure that are not the study device being assessed.

Relatedness - Device	
An event that occurs as a result of application or use of the study device being assessed.

Relationship – Not Related	
The relationship to the device or procedures can be excluded when:

Medtronic Business Restricted

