Serious Health Threat	A signal from any adverse event or device deficiency that indicates an imminent risk of death or a serious deterioration in the health in subjects, users or other persons, and that requires prompt remedial action for other subjects, users or other persons NOTE: This would include events that are of significant and unexpected nature such that they become alarming as a potential serious health hazard or possibility of multiple deaths occurring at short intervals.
Unavoidable Adverse Event (UAE)	An adverse event that is an expected, known complication or side effect occurring after a surgical procedure.

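### The Section 11.1 exemption for unavoidable adverse events makes no exception for serious or device-related events, so it conflicts with the all-AE collection rule and Table 11 and can lower both SAP 7.9.1 safety counts

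*Protocol*

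**What the plan says.** Section 11.1 of the protocol opens with a general rule: "All AE information will be collected throughout the study duration, starting during sinus surgical procedure and treatment with the Novapak device". It then gives the route: "Reporting of these events to Medtronic will occur on an AE eCRF". Sections 4.1.1.1.1 and 4.1.1.1.2 say the same for the safety endpoints: "All AEs will be collected for each subject from time of treatment until their study completion".

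Section 11.1 then makes an exemption for unavoidable adverse events (UAEs): "In all geographies, UAEs occurring post-surgery need not be reported unless the adverse event worsens or is present outside the stated timeframe post-surgery". Table 8 lists the events and their windows, from 1 to 10 days after surgery.

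Table 9 in Section 11.4 defines a UAE as follows: "An adverse event that is an expected, known complication or side effect occurring after a surgical procedure". Table 11 in Section 11.5.2 requires the investigator to send the sponsor all SAEs, and also ADEs and SADEs. None of those entries mentions UAEs. Its residual category is limited to other AEs that are reportable. Section 11.5.2 also obliges the sponsor to record any SAE. Deaths must be reported under Sections 11.1 and 11.6.

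SAP 7.9.1 evaluates safety by two counts: AEs attributed to the device or of undetermined cause, and AEs overall. The SAP does not mention UAEs.

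**The concern.** Safety is the primary objective, and the study supports a CE Mark submission. Both safety counts depend on what reaches the AE eCRF. Section 11.1 releases sites from reporting a class of early events without excluding those that are serious or caused by the device, while Table 11 requires serious and device-related events to be sent in. Two sites could treat the same event differently, each with protocol text to support it. A figure presented as the rate of all AEs would also omit a group of AEs that the protocol itself exempts.

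**Working it through.** The plan gives no expected frequency for these events, so there is no figure to reproduce. The check sets the passages side by side.

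1. **Is a UAE an AE?** Yes. The Table 9 definition says so, and the rule that all AEs are collected therefore covers UAEs. The exemption contradicts that rule unless it is read as a qualification of it, which Sections 4.1.1.1.1 and 4.1.1.1.2 do not mention.

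2. **What takes an event out of the exemption?** Only worsening, or presence outside the window. An event that is serious from its onset has not worsened. Seriousness and relatedness to the device are not listed. Death is required separately, so the gap concerns non-fatal events.

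3. **Can a Table 8 event be an SAE?** Yes. The entry "Anesthesia related complications" (2 days) has no severity limit. Nor do the entries for medication complications (2 days) and for sudden visual change or ocular swelling (1 day). An anesthesia complication within 2 days that prolongs the hospital stay fits both Table 8 and the SAE definition in Table 9.

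4. **Can a Table 8 event be an ADE?** Table 9 defines an ADE by its cause: "Adverse event related to the use of an investigational medical device". Table 8 exempts inflammation and swelling for 7 days. Section 10.1 lists inflammation, including local irritation from the product, among the risks specific to packing. Section 6.1 gives a typical residence time of 7 to 14 days, so that window falls while the device is usually in place. The event name does not show whether the cause is the surgery or the packing.

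5. **Does any sentence rank the two rules?** No. The sentence after Table 8 that points to Table 11 concerns how an immediate report may be made. It does not say that Table 11 overrides the exemption.

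6. **What happens to the counts?** The AE eCRF is the stated route to the sponsor, and under Section 11.5.1 the sponsor's review starts when an AE is received. Each omitted event lowers the overall AE count by one. It lowers the device-attributed or undetermined count by one if it belongs there, and by zero otherwise. The direction is therefore lower or unchanged for both.

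**The case against.** The strongest reply is that the two rules can be reconciled. The exemption is permissive and Table 11 is mandatory, so a site that reports complies with both. Section 9.7 tells sites to report adverse events as they occur. The sponsor must record any SAE. A UAE is tied to surgery, whereas a device-related event is an ADE with its own entry in Table 11. The residual category of Table 11 shows that the protocol expects some AEs not to be reportable. Exempting routine post-operative symptoms in an uncontrolled surgical series is a legitimate design choice.

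Most of this stands as an account of the likely intent. It does not close the gap, because no sentence states that intent. The sponsor can record only the SAEs it learns of, and the UAE definition does not exclude events caused by the device.

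There are also other routes. Subjects record AEs from Day 1, the Day 14 and Day 30 visits collect AEs (Section 9.9), and monitoring checks that Section 11 events were entered on AE eCRFs (Section 15.1). These may leave a trace. They do not settle which rule applies, and the monitoring check refers back to Section 11, where the conflict lies.

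A reader might infer that bleeding and fever overlap with packing risks in the same way as inflammation. The text does not clearly support that. Table 8 covers mild bleeding, while the packing risk in Section 10.1 is bleeding from inadequate packing or excessive bleeding that may need further control. Table 8 covers fever above 101°F, while Section 10.1 describes a medium-low grade fever. Nor does a missing severity word matter much for entries such as fatigue or nasal congestion.

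**Conclusion.** The concern holds as a conflict between reporting rules. Section 11.1 as written allows non-fatal serious or device-related early events to be left off the AE eCRF, against the all-AE collection rule and Table 11. The effect on both SAP 7.9.1 counts is downward or nil, and the overall rate is not a rate of all AEs.

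This rests on one assumption: that at least some sites would apply 11.1 literally. The size cannot be derived. The documents give no frequency for Table 8 events, and no indication of how many would be serious or device-related or of how sites would read the rule.

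A reader might infer that the protocol tells sites to withhold serious events, or that the device-related rate will be materially understated. The documents support neither. The wording permits omission without requiring it, the apparent intent is the opposite, and any numerical illustration would rest on invented event counts.

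**What to change.** Reconcile Section 11.1 with Sections 4.1.1.1.1 and 4.1.1.1.2 and with Table 11.

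- **Section 11.1:** add *This exemption does not remove the Table 11 duty to report SAEs, ADEs and SADEs on the AE eCRF.*
- **SAP 7.9.1:** label the overall AE count or rate *excluding protocol-defined UAEs not reported under 11.1*.

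The exemption for routine post-operative symptoms stays in place. The cost is one sentence and one label, with no new visit or form. The downside is a little more assessment of relatedness and seriousness for early events at sites, and possibly slightly higher reported rates.

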11.2 Device Deficiency

The DD definition is provided in **Table 9**. DD information will be collected throughout the study and reported to Medtronic. Note that DD that result in an AE to the subject should be captured as an AE only.

DD that did not lead to an AE but could have led to a SADE (i.e., if suitable action had not been taken, if intervention had not been made, or if the circumstances had been less fortunate) require immediate reporting (see **Table 11**).

11.3 Processing Updates and Resolution

For any changes in status of a previously reported adverse event or DD (i.e. change in actions taken, change in outcome, change in relatedness), information needs to be updated on, or added to the original AE or DD eCRF. All AEs must be followed until the AE has been resolved, is unresolved with no further actions planned, the subject dies or exits the study, or until study closure, whichever occurs first.

At the time of study completion, all collected adverse events that are unresolved must be reviewed and an update to the original AE must be reported.

11.4 Definitions/Classifications

Where the definition indicates “device”, it refers to only the device under investigation used in the study.

Table 9: Adverse Event and Device Deficiency Definitions

General	
Adverse Event	An untoward medical occurrence, unintended disease or injury, or untoward clinical signs in subjects, users or other

Medtronic Business Restricted

	
persons, whether or not related to the investigational medical device and whether anticipated or unanticipated.
 
NOTE: This definition includes events related to the investigational medical device.
 
NOTE: This definition includes events related to the procedures involved.
 
NOTE: for users or other persons, this definition is restricted to events related to the use of investigational medical devices.

Adverse Device Effect (ADE)	
Adverse event related to the use of an investigational medical device.
 
NOTE: This definition includes adverse events resulting from insufficient or inadequate instructions for use, deployment, implantation, installation, or operation or any malfunction of the investigational medical device.
 
NOTE: This definition includes any event resulting from use error or from intentional misuse of the investigational medical device.

Device Deficiency	
Inadequacy of a medical device with respect to its identity, quality, durability, reliability, usability, safety or performance.
 
NOTE: Device deficiencies include malfunctions, use errors, and inadequacy in the information supplied by the manufacturer including labeling.

Relatedness - Procedure	
An event that occurs as a result of the nasal sinus surgical procedure(s). This includes events involving devices used in the surgical procedure that are not the study device being assessed.

Relatedness - Device	
An event that occurs as a result of application or use of the study device being assessed.

Relationship – Not Related	
The relationship to the device or procedures can be excluded when:

Medtronic Business Restricted

	
• the event is not a known complication or side effect of the procedures, study device or product category the device belongs to or of similar devices• the event has no temporal relationship with the use of the study device or the procedures• the event does not follow a known response pattern to the study device (if the response pattern is previously known) and is biologically implausible• the discontinuation of study device application or the reduction of the level of activation/exposure - when clinically feasible – and reintroduction of its use (or increase of the level of activation/exposure), do not impact on the event• the event involves a body-site, or an organ not expected to be affected by the device or procedure• the event can be attributed to another cause (e.g. an underlying or concurrent illness/ clinical condition, an effect of another device, drug, treatment or other risk factors)• harms to the subject are not clearly due to use error 
In order to establish the non-relatedness, not all the criteria listed above might be met at the same time, depending on the type of device/procedures and the seriousness of the event.

Relationship - Possible	The relationship with the procedure or use of the study device is weak but cannot be ruled out completely. Alternative causes are also possible (e.g. an underlying or concurrent illness/ clinical condition or/and an effect of another device, drug or treatment). Cases where relatedness cannot be assessed, or no information has been obtained should also be classified as possible.
Relationship - Probable	The relationship with the procedure or use of the study device seems relevant and/or the event cannot reasonably be explained by another cause, but additional information may be obtained.

Relationship - Causal	
The event is associated with the study device or with procedures beyond reasonable doubt when:
 
• the event is a known complication or side effect of the procedure, study device, or product category the device belongs to or of similar devices• the event has a temporal relationship with the study device use/application or procedures• the event involves a body-site or organ that
◦ the study device or procedures are applied to◦ the study device or procedures have an effect on• the event follows a known response pattern to the study device (if the response pattern is previously known)• the discontinuation of the study device application (or reduction of the level of activation/exposure) and reintroduction of its use (or increase of the level of activation/exposure), impact on the event (when clinically feasible)• other possible causes (e.g. an underlying or concurrent illness/ clinical condition or/and an effect of another device, drug or treatment) have been adequately ruled out• harm to the subject is due to error in use 
In order to establish the causal relationship, not all the criteria listed above might be met at the same time, depending on the type of device/procedures and the seriousness of the event.

Serious Adverse Event (SAE)	
Adverse event that led to any of the following:
 
a) Death,b) Serious deterioration in the health of the subject, users, or other persons as defined by one or more of the following:
1) a life-threatening illness or injury, or2) a permanent impairment of a body structure or a body function including chronic diseases, or3) in-patient or prolonged hospitalization, or4) medical or surgical intervention to prevent life-threatening illness or injury or permanent

	impairment to a body structure or a body function, c) Fetal distress, fetal death, a congenital abnormality, or birth defect including physical or mental impairment. NOTE: Planned hospitalization for a pre-existing condition, or a procedure required by the CIP, without serious deterioration in health, is not considered a serious adverse event.
Serious Adverse Device Effect (SADE)	Adverse device effect that has resulted in any of the consequences characteristic of a serious adverse event.
Serious Health Threat	A signal from any adverse event or device deficiency that indicates an imminent risk of death or a serious deterioration in the health in subjects, users or other persons, and that requires prompt remedial action for other subjects, users or other persons NOTE: This would include events that are of significant and unexpected nature such that they become alarming as a potential serious health hazard or possibility of multiple deaths occurring at short intervals.
Unavoidable Adverse Event (UAE)	An adverse event that is an expected, known complication or side effect occurring after a surgical procedure.

